6.2. Magrolimab Formulation, Storage, Preparation, and Handling

Magrolimab is supplied in single-use, 10 mL vials containing 200 mg of the antibody in a formulation of 10 mM sodium acetate, 5% (w/v) sorbitol, 0.01% (w/v) polysorbate 20, at a pH of 5.0.

The labeling complies with the requirements of the applicable regulatory agencies.

CCI

Additional details about magrolimab are provided in the Pharmacy Manual.

6.3. Azacitidine Formulation, Storage, Preparation, and Handling

Single-use vials of azacitidine contain 100 mg of azacitidine and 100 mg mannitol as a sterile lyophilized powder.

CCI

. Additional details about azacitidine are provided in the Pharmacy Manual.

6.4. Dosing and Administration

The following magrolimab dosing regimen is proposed for this study:

- Priming doses of magrolimab: 1 mg/kg on Days 1 and 4; 15 mg/kg on Day 8; 30 mg/kg on Days 11 and 15; and then 30 mg/kg weekly for a total of 5 doses (on Days 22, 29, 36, 43, and 50).
- Maintenance doses of magrolimab will be 30 mg/kg on Day 57 and 30 mg/kg every 2 weeks thereafter.

Placebo will be administered as follows:

- Mirror the magrolimab dosing schedule above.

Azacitidine will be dosed according to region-specific drug labeling, either SC or IV, at the standard clinical dose of 75 mg/m² on Days 1 to 7 of a 28-day cycle in combination with magrolimab/placebo. Azacitidine may be administered on an alternative schedule of Days 1 to 5, Day 8, and Day 9 of a 28-day cycle for flexibility and convenience.

Participants should be premedicated in accordance with Section 6.5. Magrolimab, placebo, and azacitidine should be prepared as outlined in the Pharmacy Manual for the study.

The dose of each study treatment will be calculated based on actual weight at enrollment (using weight obtained either at Screening or on Cycle 1 Day 1) and remains constant throughout the study unless there is a > 10% change in weight from baseline. Dose modifications for changes in body weight $\leq 10\%$ may be made according to local institutional guidelines. In the event that a dose is modified due to a > 10% weight change, the weight on which the new dose is based, will become the new baseline weight.

When both study drugs are given on the same visit day, magrolimab/placebo will be administered at least 1 hour after the completion of azacitidine administration.

When administered IV, the total dose of azacitidine (diluted in a 50 to 100 mL infusion bag of either 0.9% sodium chloride injection or lactated Ringer's injection solution) is infused over a period of 10 to 40 minutes (refer to the azacitidine prescribing information references for detailed instructions for preparation and administration).

The duration of each magrolimab/placebo infusion including flush will be 3 hours (± 30 minutes) for the 3 doses of treatment, and then 2 hours (± 30 minutes) for infusions beyond the first 3 doses. The reduced infusion time to 2 hours is utilized based on prior data demonstrating majority CD47 RO on peripheral blood cells, thus mitigating anticipated RBC toxicities from magrolimab.

The first dose of magrolimab/placebo should be administered within 72 hours after randomization. Magrolimab/placebo doses will be given twice weekly during priming and escalation (2 weeks), with a window of ± 3 days for each dose; however, magrolimab/placebo doses are not to be given on consecutive days. If additional delay is needed to ensure a WBC of $\leq 20 \times 10^3/\mu\text{L}$, please contact the Sponsor's Medical Monitor.

During the first 28 days of treatment (Day 1, Day 4, Day 8, Day 11, Day 15, and Day 22), WBC count must be $\leq 20 \times 10^3/\mu\text{L}$ prior to each magrolimab dose. Participants with WBC $> 20 \times 10^3/\mu\text{L}$ can be treated with hydroxyurea (up to 4 g/day) throughout the study to reduce the WBC to $\leq 20 \times 10^3/\mu\text{L}$. Oral etoposide (up to 200 mg orally per day) may be given as an alternative to hydroxyurea for participants who are intolerant to hydroxyurea or cannot achieve sufficient WBC lowering on hydroxyurea.

Within 24 hours prior to each of the first 2 doses of magrolimab/placebo infusion, all participants must have a documented hemoglobin ≥ 9 g/dL. Participants who do not meet these criteria must be transfused and have their hemoglobin rechecked to meet the minimum hemoglobin threshold prior to each of the first 2 doses of magrolimab/placebo. Hemoglobin must be checked again 3 to 6 hours after the initiation of the first and second doses of magrolimab/placebo during initial treatment. The participant should be transfused as clinically appropriate. Investigators should consider additional hemoglobin monitoring during the first week of treatment in participants with symptoms of anemia or increased risk for complications of anemia.

All participants should be monitored hourly during infusion and for 1 hour after infusion for doses during the first 28 days and the repriming doses. Participants should be monitored (including measurement of vital signs, as clinically appropriate) for signs and symptoms of infusion-related reactions, which have been observed in previous magrolimab studies.

Postinfusion monitoring is not required for doses after Day 22. Participants who experience any treatment-related AEs during the observation period should be further monitored as clinically appropriate. Management of infusion-related reactions is further described in Section 7.10.1.2.

Participants may continue study treatment until they show evidence of disease progression (including treatment failure by IWG criteria or relapse after PR/CR), loss of clinical benefit, or unacceptable toxicity (further details about treatment discontinuation in Section 5.7.1).

Repriming for Magrolimab

Given the large CD47 antigen sink on normal cells, participants who have a long dose delay of magrolimab are required to be reprimed with magrolimab dosing to resaturate the CD47 antigen sink.

Repriming differs depending on where the participant is in their treatment period as follows:

- 1) For participants who have not reached Day 57 of magrolimab/placebo, a 2-week dose delay is permitted.
- 2) For participants who have received Day 57 (or beyond) of magrolimab/placebo, a 4-week dose delay is permitted.

The repriming cycles are stand-alone cycles. After Day 22 of the repriming cycle, participants should return to their original dose schedule. Table 6 illustrates the repriming magrolimab dosing regimen and schedule of assessments.

Modifications to the study treatment doses administered should be made for a > 10% change in body weight from baseline and according to local and regional prescribing standards. Dose modifications for changes in body weight $\leq 10\%$ may be made according to local institutional guidelines. In the event that a dose is modified due to a > 10% weight change, the weight on which the new dose is based, will become the new baseline weight.

Please notify the blinded Medical Monitor of any planned dose delays. If either magrolimab or azacitidine is dose delayed for > 8 weeks for any reason, the Investigator must consult with the Sponsor's Medical Monitor prior to reinitiating study treatment.

6.5. Premedication

Premedication is required prior to the administration of the first 4 doses of magrolimab/placebo and in case of repriming. Premedication during subsequent infusions may be continued based on the treating physician's clinical judgment and the presence/severity of prior infusion-related reactions. In the case of a Grade 3 infusion-related reaction, a premedication regimen for subsequent infusions is required (Section 7.10.1).

Recommended premedications are oral acetaminophen 650 to 1000 mg and oral or IV diphenhydramine 25 to 50 mg or comparable regimen. If less than 4 hours has elapsed since a prior dose of acetaminophen has been given, the dose of acetaminophen premedication may be omitted.

6.6. Neutropenic Fever Prophylaxis

Prophylactic antibiotics for the prevention of neutropenic fever are not required on study but may be administered per local institutional guidelines or Investigator discretion.

6.7. Dose Modification and Delays

6.7.1. Magrolimab/Placebo

6.7.1.1. Dose Modifications

In clinical experience with magrolimab, no significant dose-dependent toxicities have been identified. Therefore, in general, dose modifications to magrolimab/placebo should not be made. In rare circumstances, the dose of magrolimab/placebo may be reduced for \geq Grade 3 AEs that are deemed clearly related to magrolimab/placebo and not azacitidine and that do not resolve to \leq Grade 2 or baseline value within 14 days of onset. However, dose delay of magrolimab/placebo should occur first, and if the AE does not resolve, then a magrolimab/placebo dose reduction can be considered. Please notify the blinded Medical Monitor of any planned dose delays. If a magrolimab/placebo dose reduction is considered, an initial 33% dose reduction (from 30 to 20 mg/kg) should be done first. If no improvement is observed within at least 28 days, further magrolimab/placebo dose reductions from 20 to 15 mg/kg may be warranted. For persistent bone marrow hypocellularity or peripheral cytopenias (where both azacitidine and magrolimab/placebo may have a contribution), the dose of azacitidine should be reduced (see Section 6.7.2.2). Participants can re-escalate to higher doses of magrolimab/placebo up to the original 30 mg/kg dose if AEs improve, after discussion with the Sponsor's Medical Monitor.

For dose modification for $> 10\%$ change in body weight, see Section 6.4.

6.7.1.2. Treatment Delays

A treatment delay is defined as a non-protocol-specified interruption from treatment.

Treatment with magrolimab/placebo may be withheld if a \geq Grade 3 magrolimab/placebo-related AE occurs that does not resolve to \leq Grade 2 or baseline value within 14 days of onset. Magrolimab/placebo dosing may also be delayed for participants who experience hospitalization due to an AE that may preclude safe administration of magrolimab/placebo (e.g., intensive care unit admissions, significant bleeding events, severe infections, or other such events). In general, magrolimab/placebo should be continued/restarted without dose reduction. A dose delay for up to 3 days during the first 28 days may be permissible if the participant's WBC count is $> 20 \times 10^3/\mu\text{L}$ (applicable to each dose in the first 28 days: Day 1, Day 4, Day 8, Day 11, Day 15, and Day 22), to allow for oral hydroxyurea or etoposide treatment to reduce the WBC count. Magrolimab/placebo dosing may be delayed for AEs; however, starting at maintenance dose, dose delays of up to 4 weeks for other reasons may be allowed at the discretion of the Investigator and Sponsor. Participants with a treatment delay of longer than 4 weeks must undergo intraparticipant dose escalation (repriming; see Table 6 and Section 6.4) again.

Ongoing data analysis across magrolimab + azacitidine trials show that Q2W dosing of magrolimab without significant dose delays is important to yield optimal efficacy. In the event that dose delay is considered due to azacitidine related-toxicities (e.g., cytopenias) or other scenarios, magrolimab/placebo dosing should proceed as per Schedule of Assessment for treatment period - Magrolimab dosing (Table 4). Magrolimab/placebo dose may be delayed in case of serious adverse events or adverse events clearly related to magrolimab/placebo; in the event of magrolimab/placebo delay, dosing should resume as soon as it is clinically appropriate and logistically possible, without waiting to align with the participants' original Q2W schedule.

Magrolimab dosing is anticipated to coincide with azacitidine dosing. However, in the event that magrolimab dosing is decoupled from azacitidine dosing, please refer to Table 4 for assessments to be performed during the treatment visit with magrolimab dosing. Of note, in addition to assessments such as vital signs and symptom-directed physical examinations, collection of PK, ADA and peripheral blood samples for biomarker studies, in addition to other assessments specified in the Schedule of Assessments should always coincide with magrolimab dosing at time points specified in Table 4.

If either magrolimab or azacitidine is dose delayed for > 8 weeks for any reason, the Investigator must consult with the Sponsor's Medical Monitor prior to reinitiating study treatment.

If nonemergency surgical procedures are needed for participants on study treatment, magrolimab/placebo will be delayed and restarted in accordance with Table 10.

Table 10. Magrolimab/Placebo Dosing Guidance for Surgical Procedures on Study

Surgical Procedure	Magrolimab/Placebo Dose Guidance
Minimally invasive procedure (Examples: biopsies (excluding lung/liver), skin/subcutaneous lesion removal, cataract/glaucoma/eye surgery, cystoscopy)	Hold magrolimab/placebo dose 3 days prior to procedure and restart 3 days after.
Moderately invasive procedure (Examples: lung/liver biopsy, hysterectomy, cholecystectomy, hip/knee replacement, minor laparoscopic procedures, stent/angioplasty)	Hold magrolimab/placebo dose 5 days prior to procedure and restart 5 days after.
Highly invasive procedure (Examples: CNS/spine surgery, major vascular surgery, cardiothoracic surgery, major laparoscopic surgery)	Hold magrolimab/placebo dose 7 days prior to procedure and restart 7 days after.

Abbreviations: CNS = central nervous system

Finally, please notify the blinded Medical Monitor of any planned dose delays for magrolimab.

6.7.2. Azacitidine

Treatment delay of azacitidine may not occur for participants in the initial 28-day period (Cycle 1).

6.7.2.1. Treatment Delays

After the initial 28-day period, in the absence of MDS disease (as defined in Section 6.7.2.2.1), if hematologic toxicity is observed following azacitidine treatment, the next cycle of treatment should be delayed until platelets are $\geq 50 \times 10^9/L$ and neutrophils are $\geq 1.0 \times 10^9/L$ or if blood counts are improving from nadir or baseline. If recovery is achieved within 14 days, no dose adjustment is needed. However, if recovery is not achieved within 14 days, the dose should be reduced according to the azacitidine dose modification guidelines in Section 6.7.2.2.1.2. For nonhematologic AEs \geq Grade 3 that do not resolve to \leq Grade 2 or baseline value, dosing will be delayed up to 14 days from onset. If recovery is achieved within 14 days, no dose adjustment is needed. However, if recovery is not achieved within 14 days, the dose should be reduced according to the azacitidine dose modification guidelines in Section 6.7.2.2.3. Following dose modifications, the cycle duration should return to 28 days. Azacitidine dosing may also be delayed for participants who experience hospitalization due to an AE that may preclude safe administration of azacitidine (e.g., intensive care unit admissions, significant bleeding events, severe infections, or other such events).

If ≤ 2 doses of azacitidine are missed during the 7-day dosing period, dosing should continue so that the participant receives the full 7 days of treatment, as long as these additional doses are given within 1 week of the previous dose. If ≥ 3 doses of azacitidine are missed during the 7-day dosing period, the Investigator should contact the Sponsor, and a dosing decision should be made on an individual case basis.

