6.7.2.2.3. Dose Modifications Due to Nonhematologic Toxicity Irrespective of Presence of MDS Disease

Renal abnormalities ranging from elevated serum creatinine to renal failure have been reported with rare frequency in participants treated with azacitidine. In addition, renal tubular acidosis, defined as a decrease in serum bicarbonate to < 20 mmol/L in association with an alkaline urine and hypokalemia (serum potassium < 3 mmol/L), has been rarely observed. If unexplained reductions in serum bicarbonate (< 20 mmol/L) occur, the azacitidine dose should be reduced by 50% on the next cycle. Similarly, if unexplained elevations in serum creatinine or blood urea nitrogen to ≥ 2-fold above baseline values and above the ULN occur, the next cycle should be delayed until values return to normal or baseline, and the azacitidine dose should be reduced by 50%. The reduced dose should be maintained during subsequent cycles unless toxicity develops.

For other azacitidine-related nonhematologic toxicities that are \geq Grade 3 that do not resolve to \leq Grade 2 or baseline levels, azacitidine dosing should be delayed up to 14 days until resolution to \leq Grade 2 or baseline levels. If \geq Grade 3 toxicities continue despite this dose delay, dose modification of azacitidine should be performed in accordance with [Table 13](#).

Table 13. Azacitidine Dose Modification: Nonhematologic Toxicities

Toxicity	Azacitidine Dose Instruction if Recovery ^a is Not Achieved within 14 Days		
	First Occurrence ^b	Second Occurrence ^b	Third Occurrence ^b
Grade 3 or higher nonhematologic adverse event	Dose reduce azacitidine to 50 mg/m ² administered Days 1–7 per cycle AND Reassess toxicity on subsequent cycle; if still persistent despite dose delay, proceed to second occurrence.	Dose reduce azacitidine to 37.5 mg/m ² administered Days 1–7 per cycle AND Reassess toxicity on subsequent cycle; if still persistent despite dose delay, proceed to third occurrence.	Dose reduce azacitidine to 25 mg/m ² administered Days 1–7 per cycle AND Reassess toxicity on subsequent cycle; if still persistent despite dose delay, then administer azacitidine at 25 mg/m ² on Days 1–5 per cycle. Reassess toxicity on subsequent cycle. Fourth occurrence and beyond: If toxicity still persists, then contact the Medical Monitor for azacitidine dosing instructions.

a Recovery is defined as improvement of nonhematologic toxicity to \leq Grade 2 or baseline value within 14 days of dose delay.

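### The 14-day azacitidine clock for Grade 3 or higher nonhematologic toxicity starts at AE onset in Protocol Section 6.7.2.1 but at the dose delay in Section 6.7.2.2.3 and Table 13, so one event can lead to different doses

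*Protocol*

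**What the plan says.** Three places in the Protocol state the rule.

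- **Section 6.7.2.1 (azacitidine treatment delays).** The rule opens "For nonhematologic AEs" of Grade 3 or higher, with no causality condition. It says "dosing will be delayed up to 14 days from onset". Recovery within 14 days needs no adjustment. It continues: "However, if recovery is not achieved within 14 days, the dose should be reduced according to the azacitidine dose modification guidelines in Section 6.7.2.2.3".
- **Section 6.7.2.2.3, text.** This opens "For other azacitidine-related nonhematologic toxicities that are" of Grade 3 or higher, so it is limited by attribution. It says "azacitidine dosing should be delayed up to 14 days until resolution to" Grade 2 or baseline, with no mention of onset. Reduction follows only if such "toxicities continue despite this dose delay, dose modification of azacitidine should be performed in accordance with" Table 13.
- **Table 13.** The row is labelled "Grade 3 or higher nonhematologic adverse event", again without a causality condition. Footnote a defines recovery as improvement to Grade 2 or below or "baseline value within 14 days of dose delay".

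Sections 6.7.2 and 6.7.2.2 bar azacitidine delay and dose modification during Cycle 1. Section 6.7.2.2 also asks that the azacitidine guidance be applied in the same way in both arms.

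**The concern.** Azacitidine is given only on Days 1-7, or on Days 1-5, 8 and 9, of a 28-day cycle. A toxicity that begins after the last dose of a cycle can use up 14 days from onset before any dose is due. The same toxicity still has its full 14 days if the count starts when a dose is withheld. The two clocks can therefore prescribe different doses for the same participant, and Section 6.7.2.1 sends the reader to the section that holds the other clock.

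At stake is consistent handling of the backbone drug across sites. The first step in Table 13 takes the dose from 75 to 50 mg/m², a one-third cut. Under Protocol Section 5.3, an azacitidine delay also moves the Table 3 assessments, including marrow response, so delay versus reduction affects assessment timing as well as dose. The SAP reports azacitidine reductions and delays with reasons (Section 4.2.1), relative dose intensity (Section 4.2.2) and TEAEs leading to azacitidine reduction (Section 7.1.6.1). These summaries are harder to read if sites follow different clocks.

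**Working it through.** The plan gives no figure to reproduce. The check applies each wording literally to dated events, then measures how much delay the onset clock allows.

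**Step 1: azacitidine-related events.** The dates are hypothetical. A cycle is 28 days (Protocol Section 4.3), so the next cycle is due on Day 29. The onset clock ends on onset + 14. The delay clock ends on 29 + 14 = Day 43.

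| Onset | Resolved | Onset clock ends | Section 6.7.2.1 | Section 6.7.2.2.3 and Table 13 |
|---|---|---|---|---|
| Day 10 | Day 35 | Day 24 | Reduction | Delay, then full dose |
| Day 20 | Day 38 | Day 34 | Reduction | Delay, then full dose |
| Day 10 | Day 27 | Day 24 | Reduction | No change (resolved before Day 29) |
| Day 20 | Day 32 | Day 34 | Delay, then full dose | Delay, then full dose |
| Day 10 | Day 50 | Day 24 | Reduction | Reduction |

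Three of these illustrative events diverge and two do not. The dates were chosen to show both outcomes, so the split is not a frequency estimate.

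**Step 2: attribution.** Take onset on Day 10 and resolution on Day 35, but an event not related to azacitidine. Section 6.7.2.1 read alone gives a reduction. The Section 6.7.2.2.3 text gives no change under this rule. The Table 13 row with footnote a, read alone, gives a delay and then full dose.

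**Step 3: permitted delay under the onset clock.** Permitted delay = max(0, onset day + 14 − day of next scheduled dose). Assume onset is uniform over Days 1 to 28 of a cycle after the first and that the event is unresolved when the next dose is due.

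*Days 1-7 schedule.*
- Onset Days 1-6: the next dose is the following day, so 13 days each; 6 × 13 = 78.
- Onset Days 7-15: the next dose is Day 29, so 0 days; 9 of 28 onsets = 32%.
- Onset Days 16-28: 1 to 13 days, sum 91.
- Mean = (78 + 91)/28 = 169/28 = 6.0 days.

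*Days 1-5, 8 and 9 schedule.*
- Onset Days 1-4: 13 days each, sum 52.
- Onset Days 5, 6 and 7 (next dose Day 8): 11, 12 and 13 days. Onset Day 8 (next dose Day 9): 13 days. Sum 49.
- Onset Days 9-15: 0 days; 7 of 28 onsets = 25%.
- Onset Days 16-28: sum 91.
- Mean = (52 + 49 + 91)/28 = 192/28 = 6.9 days.

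The delay clock permits 14 days in every case. The longest gap from onset to next dose is 29 − 7 = 22 days with Days 1-7 dosing.

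**The case against.** The best defence is that Section 6.7.2.1 is not self-contained. Its reference to onset qualifies the length of the delay. Its reduction sentence says only that recovery must come within 14 days and then defers to Section 6.7.2.2.3, which reduces only after a delay has failed. On that reading the later section governs and there is one clock. The reading is possible, but the Protocol does not state it. Capping the delay at 14 days from onset still contradicts a 14-day delay counted from the withheld dose, and the cross-reference leads the reader to both clocks without ranking them.

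On attribution the defence is stronger. Table 13 is reached through a sentence limited to azacitidine-related toxicity, and Section 6.7.2.1 points to the same section. Section 6.7.1.1 deals separately with events clearly related to magrolimab/placebo and not azacitidine. A reader might infer that a magrolimab toxicity must also lower azacitidine. That needs Section 6.7.2.1 or the table row to be read in isolation, and the three-way split in Step 2 is a corner case. What stands is that the condition is implied in two of the three places and not stated there.

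The Step 3 figures also have limits. Uniform onset is an assumption. The percentages count all onsets, not only events that persist beyond 14 days. Doses missed within a cycle have their own rule in Section 6.7.2.1.

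**Conclusion.** The clock conflict is in the text and can change the dose that a participant receives. It affects azacitidine-related events after Cycle 1 that outlast 14 days from onset and resolve before 14 days of delay have passed. Under uniform onset the onset clock leaves no permitted delay for 32% of onsets (mean 6.0 days) or 25% (mean 6.9 days), depending on the schedule, against 14 days under the delay clock. The missing attribution condition is secondary.

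Two stronger readings are not supported. First, a reader might treat Day 29 as the next dose for every onset, which gives 15/28 (54%) with no permitted delay and a mean of 91/28 = 3.25 days. That ignores doses still due in the same cycle. Second, a reader might infer bias in CR or OS through greater azacitidine reduction in the experimental arm. The documents do not quantify any such difference. Section 6.7.2.2 requires the same guidance in both arms, not the same delivered dose. In an ITT comparison, reductions caused by the assigned regimen are part of that regimen's effect. The primary CR data were cut on 12 August 2022 (SAP Section 2.1), before Amendment 8 of 11 October 2022 (SAP Section 1), so rewording now cannot alter that analysis. Sample size, power and alpha are unaffected.

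**What to change.** Reconcile Section 6.7.2.1, the Section 6.7.2.2.3 text, the Table 13 row and Table 13 footnote a to a single start for the 14 days and a single attribution condition, worded identically in all four. Which clock and which condition apply is for the sponsor's clinical team to decide; this review does not choose.

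The change is to wording only, carried in a protocol amendment or clarification. It is not free of effort: an amendment goes to the ethics committees (Protocol Section 9.3) for approximately 200 sites (Section 4.5), so it is sensibly combined with other changes. It adds no visits and no data collection.
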